6.1.3 Product Storage and Stability

Both SUBA-itraconazole and conventional itraconazole will be stored according to the guidelines provided in the investigator brochure or package insert, respectively.

6.2 Dosage, Preparation and Administration of Study Intervention/Investigational Product

Study participants will be randomized to receive either open-label SUBA-Itraconazole or conventional itraconazole. Each treatment arm will be dosed as follows:

Arm A: Open-Label SUBA-itraconazole 65 mg Capsules – administered with food

Stage 1

- Day 1 3: two 65 mg capsules, three times daily
- Day 4 42: two 65 mg capsules, twice daily

Stage 2:

Day 43 – 180: two 65 mg capsules, twice daily.

Arm B: Conventional Itraconazole 100 mg Capsules – administered with food Stage 1:

- Day 1 3: two 100 mg capsules, three times daily
- Day 4 42: two 100 mg capsules, twice daily

Stage 2:

Day 43 – 180: two 100 mg capsules, twice daily).

Based on standard of care for invasive endemic fungal infection, some participants will be prescribed conventional itraconazole (non-study drug) after Day 180 for up to a year or beyond, as prescribed by their physician. Information for discounted itraconazole will be provided at the end of the study to help defray costs.

[figure not shown]
6.3 Modification of Study Intervention/Investigational Product for a Participant

Dose increase, reduction or cessation is permitted at the discretion of the investigator. Any modification to the dosing regimen will be noted in the source document and entered into the eCRF.

The Investigator will consider a dose modification For the following combined drug levels (itraconazole + hydroxyitraconazole) at Day 14 and Day 42:

- <500ng/ml increase dose

- >5000ng/ml decrease dose

Any modification to the dosing regimen should have blood-levels re-analyzed every two weeks until the target therapeutic level is achieved (see schema below).

The Investigator will consider dose reduction and/or dose cessation for toxicity if the participant:

- Develops a study drug-related, grade 4 adverse event
- Develops a study drug-related, serious adverse event (SAE)
- Develops dose-limiting study drug-related toxicity despite dose-reduction.

6.4 Accountability and Assessment of Subject Compliance with Study Intervention/Investigational Product

Study drug accountability procedures will be performed by the clinical site. The site will maintain all product per storage guidelines highlighted in the product insert or IB. The clinical site will document receipt, dispensing, and any unused product. This documentation will be maintained throughout the conduct of the study.

Study drug compliance will be assessed at each visit (Day 7, Day 14, Day 28, Day 42, Day 84, Day 180). Subjects will bring all containers and unused medication (if applicable) to each visit. Sites will determine the total amount of product dispensed and compare it to returned product. This information will be collected on the source documents and entered into the eCRF.

6.5 Concomitant Medications/Treatments

6.5.1 Collection

Concomitant medications will be collected from signing of informed consent all the way through to the end of study visit. Any medications taken within 2 weeks of Study Day 1, even if prior to ICF collection date, should be noted.

6.5.2 Restricted Concomitant Medications

Itraconazole may affect the plasma concentration of other drugs, as it is an inhibitor of CYP3A4 as well as P-gp (P-glycoprotein). Sites should carefully evaluate concomitant medication use to ensure that possible drug interactions do not affect the health of the patient.

Drugs that may decrease plasma concentrations of itraconazole include:

| Category | Examples |
|--|---|
| Anticonvulsants | carbamazepine, phenobarbital, phenytoin |
| Antimycobacterials | isoniazid, rifabutin, rifampin |
| Non-Nucleoside Reverse Transcriptase Inhibitors | nevirapine |

GI Medications

Additionally, certain anti-acids, H2 blockers, and protein pump inhibitors are prohibited with conventional itraconazole. If possible, H2 blockers and protein pump inhibitors should be stopped 7 days prior to enrollment, at the discretion of the treating physician. Anti-acids may be taken 1-2 hours AFTER oral dosing with study drug.

Drugs that can increase plasma concentrations of itraconazole include:

| Category | Examples: |
|-----------------------|------------------------------|
| Macrolide Antibiotics | clarithromycin, erythromycin |
| Protease Inhibitors | indinavir, ritonavir |

Alternative fungal medications administered for more than 14 days prior to the first dose of study medication are prohibited unless subject with coccidioidomycosis previously treated with fluconazole therapy for more than 14 days. If in the opinion of the investigator, the subjects with coccidioidomycosis are having an inadequate response or, are intolerant of fluconazole (e.g.due to adverse events), the subjects may be included. Such subjects must washout from fluconazole for 7 days (~5 half-lives of fluconazole) before starting investigational therapy.

7 STUDY SCHEDULE

7.1 Screening

Patients presenting to the clinic or hospital with new onset presumed or definite endemic fungal infection that have not been treated with an alternative antifungal medication for more than 14 days prior to study drug administration; and with no known exclusion criteria by medical history will be given informed consent to enroll in the study.

7.2 Enrollment/Baseline

Patients consenting to the study will be further evaluated for inclusion and exclusion criteria, medical history, physical examination, pregnancy test (blood or urine BHCG), mycologic assessment, antigen and antibody levels, radiography (if clinically indicated); serum chemistry, serum hematology. See Appendix A for study procedures per visit.

7.3 Follow-up

Participants will be assessed in clinic at Day 7, Day 14, Day 28 (1 month), Day 42, Day 84 (3 months) and Day 180 (6 months). In the opinion of the investigator, clinic visits may be replaced with telemedicine visits or home visits, with allowances made for blood draws at remote or commercial laboratories. Documentation in source documents should clearly define accommodations in visit locations or methods when attempting to protect participants and other patients from potential exposure and hazards related to COVID-19. The Day 7, 14 and 42 visits allow a narrow window (+/- 3 days) so that accurate PK levels can be drawn.

The Day 84 and 180 visits will allow a window of (+/- 7 days).

At each visit, blood samples will be drawn for study-specific safety and efficacy labs. In addition a quality of life questionnaire will be administered at Day 42. See Appendix A for study procedures per visit.

7.4 Final Study Visit or Early Termination Visit

The final study visit will occur at Day 180 (with a window of +/-7 days). During this visit, a physical examination, vital signs, quality of life questionnaire, assessments of concomitant medications and adverse events and mycological assessments will take place. Blood and urine samples will be drawn for study-specific safety and efficacy labs. See Appendix A for study procedures per visit.

7.5 Unscheduled Visit

If clinically indicated, study subjects may be asked to return to clinic to further assess safety issues, resolution of a safety issue, evaluate treatment compliance, or other reasons as determined by the investigator.

8 STUDY PROCEDURES/EVALUATIONS

8.1 Clinical Evaluations

- 1. Medical history will be obtained by interview and if available, from medical records.
- Medications history includes medications taken within the prior 2 weeks and indication. Assessment of eligibility should include a review of permitted and prohibited medications.
- 3. Physical examination will be conducted at baseline, targeted physical exams may occur with vital signs at each subsequent visit. At end of therapy or early termination, a physical examination is required.

8.2 Laboratory Evaluations

Safety laboratory evaluations (Hematology, Biochemistry and Urine Pregnancy Tests) will be conducted by the local site laboratory as part of standard of care for treating patients with endemic mycoses.

8.2.1 Clinical Laboratory Evaluations

- 8.2.1.1 Hematology: hemoglobin, hematocrit, white blood cells (WBC) with differential count, platelet count.
- 8.2.1.2 Biochemistry: creatinine, total bilirubin, alanine aminotransferase (ALT), aspartate aminotransferase (AST).
- 8.2.1.3 Blood or Urine Pregnancy test, to be done within 24 hours prior to study intervention and results must be available prior to administration of study product.
- 8.2.1.4 HIV: HIV Testing must be performed and resulted no more than 30 days prior to start of study unless previous positive findings are documented in source documents.

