2.3 Potential Risks and Benefits

2.3.1 Potential Risks

All medical treatments have the potential of causing undesirable effects. For this reason, the study is performed under carefully controlled conditions.

Common side effects reported to date in patients taking conventional itraconazole (reported in 1-10% of the patients):

- Vomiting
- Diarrhea
- Abdominal pain
- Anorexia
- Edema
- Fatigue
- Fever
- Malaise
- Rash*
- Pruritus

- Headache
- Dizziness
- Libido Decreased
- Somnolence
- Hypertension
- Hypokalemia
- Albuminuria
- Hepatic Function Abnormal
- Impotence

Nausea (11%) is a common side effect (reported in more than 10% of patients) associated with other marketed azoles that may or may not be associated with SUBA-Itraconazole.

Common side effects that were reported in less than 10% of patients taking other marketed azoles (fluconazole, voriconazole, itraconazole, ketoconazole, posaconazole, isavuconazole) were:

- Dizziness
- Chest pain
- Flatulence
- Sleeplessness
- Liver function test abnormalities
- Renal insufficiency

- Trouble Breathing
- Digestion problems
- Tremors
- Asthenia (weakness)
- Cardiovascular problems such as tachycardia or arrhythmia
- Vision disturbances

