8.4 Methods and Timing for Assessing, Recording, and Analyzing Safety Parameters

8.4.1 Adverse Events

ICH E6 defines an AE as any untoward medical occurrence in a patient or clinical investigation subject administered a pharmaceutical product regardless of its causal relationship to the study treatment. An AE can therefore be any unfavorable and unintended sign (including an abnormal laboratory finding), symptom, or disease temporally associated with the use of medicinal (investigational) product. The occurrence of an AE may come to the attention of study personnel during study visits and interviews of a study recipient presenting for medical care, or upon review by a study monitor.

All AEs including local and systemic reactions not meeting the criteria for "serious adverse events" should be captured on the appropriate CRF. Information to be collected includes event description, time of onset, clinician's assessment of severity, relationship to study product (assessed only by those with the training and authority to make a diagnosis, which would include MD, PA, Nurse Practitioner, DO, or DDS), and time of resolution/stabilization of the event. All AEs occurring while on study must be documented appropriately regardless of relationship. All AEs will be followed to adequate resolution.

Any medical condition that is present at the time that the patient is screened should be considered as baseline and not reported as an AE. However, if it deteriorates at any time during the study, it should be recorded as an AE.

All AEs must be graded for severity and relationship to study product.

FDA defines an AE as any untoward medical occurrence associated with the use of a drug in humans, whether or not considered drug related.

Severity of Event: All AEs will be assessed by the clinician using a protocol defined grading system. For events not included in the protocol defined grading system, than the following guidelines will be used to quantify intensity.

- Mild: events require minimal or no treatment and do not interfere with the patient's daily activities.
- Moderate: events result in a low level of inconvenience or concern with the therapeutic measures. Moderate events may cause some interference with functioning.
- Severe: events interrupt a patient's usual daily activity and may require systemic drug therapy or other treatment. Severe events are usually incapacitating.

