10.3 Study Outcomes

Stage I- Randomized Open-Label, Parallel Group

Primary Endpoints

- 1. Pharmacokinetic superiority at Day 14
 - a) Inter- and intra- patient variability: Time to attain therapeutic plasma concentrations of itraconazole (> 500 mcg/L)
 - b) Interpatient variability as calculated by co-efficient of variation

Trough (pre-morning dose) sample will be collected at Days 14 and 42. Using validated LC-MS/MS methods, blood samples will be analyzed to quantify plasma concentrations of itraconazole and hydroxyitraconazole.

Participants should arrive to the trial site having **not** taken their morning dose of study drug.

Note: site investigators are discouraged from drawing independent PK laboratories to check itraconazole levels outside of the designated timepoints (Day 14)

2. Tolerability - ability to remain on study drug at Day 42 with less than a 7-day interruption of therapy

Secondary Endpoints

- PK at day 7 plasma concentrations of itraconazole- (comparative trough, steady state plasma itraconazole concentrations of SUBA-itraconazole 65mg capsules with food to itraconazole 100mg capsules with food over 7 days)
- 2. PK at day 42 plasma concentrations of itraconazole- (comparative trough, steady state plasma itraconazole concentrations of SUBA-itraconazole 65mg capsules with food to itraconazole 100mg capsules with food over 42 days)
- 3. Efficacy: clinical outcomes (time to relief of fungal signs and symptoms) at days 14, 28, and 42
- 4. Safety- defined as: adverse events that occurred in each study arm by Day 42
- 5. Tolerability ability to remain on study drug at Days 14 & 28
- 6. Days of Hospitalization and ICU stays at Day 42
- 7. Other health economic endpoints:
 - 1. Number of unscheduled procedures (i.e., labs, scans, etc.) at Day 42
 - 2. Total number of capsules taken at Day 42
 - 3. SF-20 (QOL) assessments at Day 42

Stage II- Open-Label, Extension

Primary Endpoint

- 1. Efficacy- Free from proven or probable invasive endemic fungal infection at Day 180
- 2. Tolerability- ability to stay on study drugs at Days 43 180.

Secondary Endpoints

- 1. Safety- Adverse events that occurred in each study arm between Days 43 180 or end of therapy
- 2. Days of Hospitalization (Days 1 180) defined as days of hospitalization and ICU stays from randomization to Day 180 or end of therapy)

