APPENDIX A: SCHEDULE OF EVENTS

| Activities | Day 1 ^g (Baseline) | Day 7 (1 wk) +/- 3 days | Day 14 (2 wks) +/- 3 days | Day 28 (4wks) +/- 7 days | Day 42 (6 wks) +/- 3 days | Day 84 (3 mos) +/- 7 days | Day 180 (6 mos) +/- 7 days |
|---|----------------------------------|----------------------------------|------------------------------------|-----------------------------------|------------------------------------|------------------------------------|-------------------------------------|
| Informed Consent | Х | | | | | | |
| Review of Inclusion/Exclusion Criteria | × | | | | | | |
| Randomization | X | | | | | | |
| Medical History | X | | | | | | |
| Clinical Assessment: vital signs, PE ^a , & radiographs ^b ; | × | Х | Х | Х | Х | Х | × |
| Participant Administered SF-12 Quality of Life Survey | Х | | | | Х | | х |
| Tolerability | Х | | | Х | Х | | Х |
| βHCG - pregnancy test ^c | Х | | | | | | |
| Mycologic Assessment: clinical, urine and serum quantitative antigen levels^d & serum antibodies ^{e,f} | х | | х | Х | Х | Х | х |
| Serum and Urine for future use: blood, urine, saliva, sputume | X | | Х | X | Х | Х | Х |
| Plasma PK ^f | | Χ | Х | | Х | | |
| Chemistry: Creatinine, AST and Alkaline Phosphatase, Total Bilirubin ^f | Х | | Х | Х | Х | Х | х |
| Hematology: CBC with Differential ^f | X | | | X | | X | X |
| HIV Status: Documentation of any positive test; Documentation of Negative test 30 days or less prior to start of study drug. | Х | | | | | | |
| Antifungal Therapy (Pre- and during study) | Х | Х | Х | Х | Х | Х | Х |
| Dose Modifications | | | Х | X | Х | Х | |
| Study Drug Dosing & Accountability | Х | Х | Х | Х | Х | Х | Х |
| Concomitant Therapy | Х | Х | Х | Х | Х | Х | Х |
| Adverse Events | Х | Х | Х | Х | Х | Х | Х |
| Days of Hospitalization, ICU | Х | Х | Х | Х | Х | Х | Х |

^a Complete physical exam on baseline; targeted physical exams for all other visits.

b Radiograph results that were performed as standard of care to diagnose or assess the fungal infection.

^C Urine or Serum pregnancy test is acceptable.

^d Histoplasma and Coccidioides urine and serum quantitative antigen.

^e Collection of sputum, if associated with the IFI and available.

^fChemistry and hematology will be processed at the site for safety evaluations; PK samples will be sent to a central lab for processing; see Manual of Procedures for specimen handling procedures;

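### Hypokalemia is listed as a known effect of the comparator, but potassium is in neither chemistry panel, so the adverse-event comparison may under-count it

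*Combined protocol and SAP*

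**What the plan says.** Section 2.3.1 introduces one list of effects with "Common side effects reported to date in patients taking conventional itraconazole (reported in 1-10% of the patients"). Hypokalemia is on that list, and so is abnormal hepatic function.

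The laboratory plan names its chemistry analytes in two places:

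- Section 8.2.1.2: "creatinine, total bilirubin, alanine aminotransferase (ALT), aspartate aminotransferase (AST").
- Appendix A: "Chemistry: Creatinine, AST and Alkaline Phosphatase, Total Bilirubin", marked for Days 1, 14, 28, 42, 84 and 180.

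Section 7.2 names no analytes for baseline. It asks for "serum chemistry, serum hematology. See Appendix A for study procedures per visit". Section 8.2 says that the safety tests "will be conducted by the local site laboratory as part of standard of care for treating patients with endemic mycoses".

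On the analysis side, section 8.4.1 defines an adverse event to include "any unfavorable and unintended sign (including an abnormal laboratory finding), symptom, or disease". Section 10.3 defines Stage I safety as "adverse events that occurred in each study arm by Day 42" and has a matching endpoint for Days 43 to 180. Section 10.5 says that events will be compared between arms.

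**The concern.** An abnormal laboratory value counts as an adverse event, and adverse events by arm are the safety endpoint in both stages. A laboratory effect that the protocol itself attributes to the comparator therefore falls within the endpoint, yet no required test would reveal it. Abnormal hepatic function, from the same list, is covered in both panels by bilirubin and at least one transaminase. The plan gives no reason for treating the two differently.

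Three things are at stake. First, the count of hypokalemia may be too low. Second, whether a case is found may depend on the habits of about 20 sites in several countries. Third, no baseline potassium is required. Section 8.4.1 treats a condition present at screening as baseline and not as an adverse event unless it worsens, so a low value found later by chance may be impossible to classify. A silent low value may also go unseen over 180 days of treatment.

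**Working it through.** **Step 1. Compare the lists.**

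| Analyte | Section 8.2.1.2 | Appendix A |
|---|---|---|
| Creatinine | yes | yes |
| Total bilirubin | yes | yes |
| AST | yes | yes |
| ALT | yes | no |
| Alkaline phosphatase | no | yes |
| Potassium | no | no |

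Section 7.2 adds nothing, because it defers to Appendix A. Nothing suggests redaction or a broken table: both lists read as complete.

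**Step 2. The plan's only power figure.** Section 10.2 gives 77% power for the PK comparison. With an assumed 40 per arm, the standard error is √(94.0²/40 + 101.8²/40) = √(220.9 + 259.1) = 21.9, and 60.0/21.9 = 2.74. The unequual-variance t-test then has 77.2% power, so the stated figure reproduces. It concerns PK and does not bear on safety counts.

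**Step 3. Expected cases.** Inputs: 80 randomized (section 10.2); 40 per arm, which is an assumption because no allocation ratio is stated; and the 1-10% band (section 2.3.1). The band belongs to the whole list and to conventional itraconazole. The documents give no specific rate for hypokalemia and none for SUBA-itraconazole.

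- Expected cases = 40 × rate: 40 × 0.01 = 0.4 and 40 × 0.10 = 4.
- Chance of at least one case = 1 − (1 − rate)^40.
- If only half of cases are detected (an assumption for illustration), the rate is halved.

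| True rate | Expected cases, all detected | Chance of at least one | Expected recorded, half detected | Chance of at least one recorded |
|---|---|---|---|---|
| 1% | 0.4 | 33% | 0.2 | 18% |
| 5% | 2 | 87% | 1 | 64% |
| 10% | 4 | 98.5% | 2 | 87% |

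**Step 4. What full measurement would do for a test.** Suppose every case were found and the arms split 4 of 40 against 0 of 40. The two-sided Fisher p-value is 2 × C(40,4)/C(80,4) = 2 × 91,390/1,581,580 = 0.116. For true rates of 10% and 1%, Fisher's exact test (which section 10.1 allows) has about 15% power at 40 per arm; a normal approximation gives about 42%. For 10% against 5%, the Fisher power is about 4%. Adding potassium therefore improves the record of events, not the ability to establish a difference.

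**The case against.** The strongest reply is that cases can still come to light. Safety laboratory work is local and part of routine care, so many sites may run potassium anyway. Adverse events and hospital days are collected at the scheduled visits, and any abnormal result that is found must be recorded whatever its cause. This stands. A reader might infer that hypokalemia will be found only if a clinician who knows the treatment orders the test. The documents do not support that: routine local panels, symptoms and hospital care are all open routes. What remains is that none of these routes is required or uniform.

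A reader might also infer that open-label treatment will make detection unequal between arms. The documents do not show this. Both arms receive oral itraconazole on the same visit and laboratory schedule, and nothing gives a site a reason to check potassium more often in one arm. Unequal detection is possible, but there is no basis for putting a figure on it.

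It is also fair to say that safety is a secondary endpoint, that no hypothesis concerns potassium, and that no passage promises to measure every listed effect. The omission is a gap in a design choice and not a contradiction. The Manual of Procedures, which is not among the documents, could specify more analytes. However, both lists name their analytes, and the Appendix A footnote on chemistry and PK samples refers to the Manual for specimen handling.

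Finally, albuminuria is on the same list and no urinalysis is scheduled. Urine protein would be a new test, not an addition to an existing sample, so it is not part of this point.

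**Conclusion.** The point holds in a limited form. Hypokalemia is a listed effect of the comparator and is not measured systematically. The by-arm adverse-event comparison may under-count it, and no baseline value is required to tell new from pre-existing low potassium.

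The size is modest: about 0.4 to 4 cases in the conventional arm, assuming 40 patients per arm and applying the protocol's general 1-10% band to this one effect. The amount of under-counting is unknown, because it depends on how often sites measure potassium of their own accord. The benefit of a change is complete and uniform ascertainment, and patient safety. It does not rescue a between-arm test, and no primary conclusion depends on it. The finding does not establish bias for or against either arm.

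**What to change.** Add serum potassium to the biochemistry list in section 8.2.1.2 and to the Appendix A chemistry row, run on the samples already scheduled for Days 1, 14, 28, 42, 84 and 180. The Day 1 value supplies the missing baseline.

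The cost is one extra analyte at the local laboratory, an eCRF field and a protocol amendment, which section 13.2 requires each institution's review board or ethics committee to approve before use. No extra visit or blood draw is needed. The same two lines also disagree on ALT and alkaline phosphatase. That is a separate matter, but it can be reconciled in the same amendment. No treatment rule is proposed.
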